### 3.4 Framework

A superiority hypothesis testing framework will be used, in which we will compare whether the Booster intervention is superior to the usual care.

### 3.5 Statistical analyses and stopping guidelines

No pre-specified interim analyses are performed, and therefore, a stopping guidance was not applicable.

### 3.6 Timing of final analysis

The final analyses will be performed after the finalization of the data collection and processing of the primary and secondary outcomes.

### 3.7 Timing of outcome assessment

The primary and secondary outcomes will be assessed at baseline and post intervention (3 weeks).

## 4. Statistical principles

### 4.1 Confidence intervals and P values

All statistical tests will be two-tailed. P for significance will be set at 0.05 and 95% confidence intervals will be estimated.

### 4.2 Adherence and protocol deviations

For participants randomized to the Booster-arm, the adherence will be assessed by counting the number of valid wear days of the activity tracker ( $\geq 10$  h/day), and by dividing the number of valid days by the total number of days of the intervention period  $\times 100\%$ .

The adherence to the daily use of the activity tracker will be reported as the mean  $\pm$  standard deviation (when normally distributed) or as median [interquartile range] (when not-normally distributed).

All protocol deviations made to the protocol (e.g. change in pre-defined inclusion/exclusion criteria, baseline and post-intervention, data cleaning/processing) will be reported and described.

#### 4.3 Analysis populations

We plan to do an intention-to-treat analysis. This analytical cohort includes all randomized participants. With this approach, all randomized participants are included in the analysis, based on the groups to which they were initially randomly assigned. This imply that some participants will have valid data in both time points, while some might have missing data at baseline or post-intervention assessment.

### 5. Trial population

#### 5.1 Screening Data

No screening was needed as participants who participated in the intervention group during the original SIT LESS study were eligible for inclusion.

#### 5.2 Eligibility

Eligible patients were defined on the inclusion and exclusion criteria. In general, patients with coronary artery disease who followed cardiac rehabilitation with a special sedentary reduction program (SIT LESS) were included. Specific inclusion and exclusion criteria are:

Inclusion Criteria:

1. Participation in the SIT LESS intervention group of the original SIT LESS study. Inclusion criteria of the SIT LESS study were:
  - a. Patients aged  $\geq 18$  years old
  - b. Referred to CR because of stable CAD, an acute coronary syndrome, and/or after coronary revascularization.

Exclusion Criteria:

1. Unable to give informed consent.
2. Wheelchair-bounded / not physically able to stand or walk.
3. Dutch Language barrier.
4. Coronary arterial bypass graft surgery expected within 8 weeks after inclusion.
5. New York Heart Association class III or IV heart failure.
6. Participation in another interventional study targeting sedentary behavior or physical activity.

#### 5.3 Recruitment

A CONSORT flow diagram will be used to summarize the number of patients who were:

---

- Eligible for study participation based on participation in the SIT LESS study without dropping out.
- Approached for study participation (Reasons for no approach will be given\*).
- Included in the study.
- Randomized.
- Received the randomized allocation .
- Did not receive the randomized allocation\*.
- Lost to follow-up\*.
- Discontinued the intervention\*.
- Randomized and included in the primary analysis.
- Randomized and excluded from the primary analysis\*.

\*reasons will be provided

#### 5.4 Withdrawal/follow-up

The number, timing, and reasons (e.g. adverse events, lost motivation to continue with the study, withdraw consent, could not or did not want to attend to the post-intervention evaluations) for withdrawal will be noted and described.

#### 5.5 Baseline patient characteristics

A baseline table will be created to describe the characteristics of the study population. The characteristics include participant characteristics (e.g. age, gender, body mass index, alcohol use, smoking), disease characteristics (e.g. comorbidities, medication use) and objectively measured sedentary behavior and physical activity levels. The characteristics of the total study population and each study arm will be summarized using mean (SD) or median (interquartile range) for normally and not normally distributed continuous variables, respectively, and as number (percentage) for categorical variables.

### 6. Analysis

#### 6.1 Outcome definitions

##### Primary outcome

Change in daily ST (h/day; baseline and post-intervention).

ST is objectively assessed using a validated accelerometer (ActivPALmicro, PAL Technologies Ltd., Glasgow, United Kingdom). The ActivPAL is a small device (25x45x5 mm), waterproof attached to the participant's thigh using hypoallergenic tape. The ActivPAL combines a tri-axial accelerometer with an inclinometer which accurately distinguishes between sitting, standing and walking. Participants are instructed to wear the ActivPAL 24 h/day for 8 consecutive days and to fill in a diary with sleep times and moment of attachment and detachment. Raw data is analyzed by a modified version of the script of Winkler et al.. Total ST (Metabolic Equivalent of Task score (METs)  $\leq 1.5$  while awake in a sitting, lying or reclining posture) is expressed in h/day.

##### Secondary outcomes

- Change in number of prolonged sedentary (bouts/day; baseline and post-intervention). Prolonged sedentary bouts are defined as an accumulation of ST ( $\geq 30$  min) and based on ActivPAL data.

- Prevalence of an average ST >9.5 h/day (number, (%); baseline and post-intervention). Daily ST will be dichotomized using 9.5 h/day as cut-off as it was previously shown that exceeding this upper limit of normal was associated with an increased risk of morbidity and mortality. ActivPAL data will be used for this outcome.
- Change in the prevalence of a sitting time  $\geq 9.5$  h/day.
- Change in daily time spent in light-intensity physical activity (LIPA in h/day; baseline and post-intervention). The ActivPAL data will be used and LIPA is categorized as physical activity with MET levels < 3.
- Change in daily time spent in moderate-to-vigorous intensity physical activity (MVPA in h/day; baseline and post-intervention). The ActivPAL data will be used and MVPA is categorized as physical activity with MET levels  $\geq 3$ .
- Change in step count (steps/day; baseline and post-intervention). The ActivPAL data will be used for this outcome.

## 6.2 Analysis methods

The primary and secondary outcome analyses will be performed on an intention-to-treat basis using a constrained (i.e. baseline adjusted) linear mixed-model analysis to handle missing data and to avoid baseline imbalances between treatment arms. Time (categorical) and time\*group will be included in the model. In addition, we evaluate the difference between the control and Booster group in the proportion of participants with ST  $\geq 9.5$  h/day post-intervention by constrained logistic mixed model analysis.

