- CIBEROBN Physiopathology of Obesity and Nutrition, Granada, Spain
- Faculty of Sport and Health Sciences, University of Jyväskylä, Jyväskylä, Finland.

[name], MD, full professor

- Department of Medical BioSciences, Radboud university medical centre, Nijmegen, The Netherlands

[name], PhD, full professor

- Department of Medical BioSciences, Radboud university medical centre, Nijmegen, The Netherlands
- Research Institute for Sports and Exercise Sciences, Liverpool John Moores University, Liverpool, United Kingdom

2. Trial Summary

Official Title: Remote 3-week Booster Intervention to Reduce Sedentary Time in Patients With Coronary Artery Disease: A randomized controlled trial

Brief title: BOOSTSITLESS

ClinicalTrials.gov ID: NCT06038188

Study ID: NL72604.091.20

Brief Summary: The BOOSTSITLESS is a randomized controlled trial designed to examine the effects of a 3-week remote Booster intervention on changes in sedentary time among cardiac rehabilitation graduates.

Keywords: Cardiac rehabilitation; e-Health; prevention; sitting; physical activity; cardiovascular disease.

Detailed summary:

Introduction: Previous studies revealed that sedentary time (ST) can effectively be targeted in patients with coronary artery disease (CAD) participating in cardiac rehabilitation (CR). However, only transient effects were observed, as patients relapsed to a sedentary lifestyle in subsequent months. We examined the effectiveness of a 3-week remote Booster intervention on changes in ST among CR graduates.

Methods: CAD patients previously completing CR with a ST reduction program (1.5-2.5 years ago) were included in this randomized controlled trial (1:1, stratified for gender). All participants received usual care, whereas Booster participants additionally received a 3-week remote behavioral change intervention consisting of education, goal-setting, motivational interviewing, and telemonitoring. The primary outcome was the change in accelerometer-derived ST from baseline to post-intervention and secondary outcomes included changes in ST and physical activity characteristics. A baseline constrained linear mixed-model was performed.

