- Change in number of prolonged sedentary (bouts/day; baseline and post-intervention). Prolonged sedentary bouts are defined as an accumulation of ST (≥ 30 min) and based on ActivPAL data.
- Prevalence of an average ST > 9.5 h/day (number, (%); baseline and post-intervention). Daily ST will be dichotomized using 9.5 h/day as cut-off as it was previously shown that exceeding this upper limit of normal was associated with an increased risk of morbidity and mortality⁶. ActivPAL data will be used for this outcome.
- Change in the prevalence of a sitting time ≥ 9.5 h/day.
- Change in daily time spent in light-intensity physical activity (LIPA in h/day; baseline and post-intervention). The ActivPAL data will be used and LIPA is categorized as physical activity with MET levels < 3 .
- Change in daily time spent in moderate-to-vigorous intensity physical activity (MVPA in h/day; baseline and post-intervention). The ActivPAL data will be used and MVPA is categorized as physical activity with MET levels ≥ 3 .
- Change in step count (steps/day; baseline and post-intervention). The ActivPAL data will be used for this outcome.

9. Sample calculations and statistical analysis

Sample size.

As our study has an explorative character, no formal sample size calculation was performed prior to trial initialization. Before the original SIT LESS study, a sample size calculation was performed and described³². Based on that calculation, 106 patients were needed in the SIT LESS arm of the trial. Participants in this study arm will be eligible for participation in the BOOSTSITLESS.

In the original SIT LESS study, we found an effect size Cohen D of 0.3²⁸ with an alpha of 0.05 and beta of 0.2 (power 0.8). The estimated sample size, based on previously mentioned parameters and repeated-measures ANOVA, needed for this study was 24 participants (12 in each study arm)(Figure 2).

[figure not shown]

Figure 2. Sample size calculation using G*power (version 3.1)

Statistical analyses.

The treatment effects will be tested using baseline constrained mixed models (i.e. adjusting for baseline of the outcome studied) for the study outcomes using an intention-to-treat approach as primary analysis. A detailed Statistical Analysis Plan has been developed in a separate document that will be available.

10. Treatments/Interventions

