### 3.2 Randomization

The researcher randomly allocates (1:1) the participant into the control or Booster group with allocation concealment in random block sizes ranging from two to six participants, using a computerized algorithm (Castor Electronic Data Capture 2021, Ciwit B.V., Amsterdam, The Netherlands). Randomization is stratified by gender to ensure balance of the treatment arms. Due to the nature of the intervention, the research team and participants are not blinded to the treatment allocation. The outcome assessment of ST is blinded for the research team as an automatized script is used based on a unique participant identification number, independent from the randomization procedure.

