### 3.3 Sample Size

As our study has an explorative character, no formal sample size calculation was performed prior to trial initialization. For the original SIT LESS study, a sample size calculation was performed and described. Based on that calculation, 106 patients were needed in the SIT LESS arm of the trial. Participants in this study arm will be eligible for participation in the BOOSTSITLESS.

In the original SIT LESS study, we found an effect size Cohen D of 0.3 with an alpha of 0.05 and beta of 0.2 (power 0.8). The estimated sample size, based on previously mentioned parameters and repeated-measures ANOVA, needed for BOOSTSITLESS was 24 participants (12 in each study arm)(**Figure 2**) suggesting that the included sample size (n=42) is large enough to run meaningful analyses.

**Figure 2.** Sample size calculation using G\*power (version 3.1)

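### Gender is the randomisation stratum but is in none of the planned models; if it predicts post-intervention sedentary time beyond baseline, the standard error is overstated and a little power is lost

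*SAP*

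**What the plan says.** SAP 3.2 states: "Randomization is stratified by gender to ensure balance of the treatment arms". Allocation is 1:1, "with allocation concealment in random block sizes ranging from two to six participants". The Protocol's Trial Summary agrees: "1:1, stratified for gender".

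For the constrained linear mixed model, SAP 6.2 lists the terms in one sentence: "Time (categorical) and time\*group will be included in the model". The logistic mixed model for ST of at least 9.5 h/day is given no further covariates. Protocol 9 describes the same approach: "The treatment effects will be tested using baseline constrained mixed models (i.e. adjusting for baseline of the outcome studied". Apart from the stratification, gender appears only as an item for the baseline table (SAP 5.5). Neither document puts it in a model or says why it is omitted.

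**The concern.** Stratifying by gender nearly removes chance gender imbalance from the true sampling variability of the arm difference. A model that contains gender takes account of this. A model without it still counts gender-related variation in ST as unexplained noise, so it reports a standard error larger than the estimate really has.

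The baseline constraint helps only in part. It removes whatever gender effect is already visible in baseline ST, and leaves any gender effect on post-intervention ST at a given baseline ST. If there is no such remainder, nothing is lost. If there is, the confidence interval is too wide, the test runs below its nominal 5%, and power falls. This sentence of SAP 6.2 governs the primary outcome and every continuous secondary outcome, in a trial of 42 people.

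**Working it through.** **The plan's own figure.** SAP 3.3 and Protocol 9 give a required total of 24. The G*Power figure is not shown, so the settings are assumed: a repeated-measures within-between interaction, two groups, m=2 visits, f=0.3, ρ=0.5. Then λ = N·f²·m/(1−ρ) = 24 × 0.09 × 2 / 0.5 = 8.64 on 1 and 22 df, and power is 0.802. So 24 reproduces if 0.3 is entered as Cohen f. If 0.3 is Cohen d, as the text says, f=0.15, the same calculation gives N=90, and power at n=42 is about 0.48. That is a separate matter; here it shows only that spare power cannot be taken for granted.

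**Inputs for this check.** From the documents: n=42 (SAP 3.3), 1:1 allocation in blocks of two to six within gender (SAP 3.2), two-sided 5% (SAP 4.1), two visits (SAP 3.7). Assumed, because the documents do not give them: 10 of 42 in the smaller gender stratum, within-gender SD 1, baseline-post correlation ρ=0.6 (range 0.4 to 0.8), true effect 0.6 SD at ρ=0.6 (0.687 and 0.450 at ρ=0.4 and 0.8, to keep power near 64-65%).

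**Closed form.** With p = 10/42 = 0.238, p(1−p) = 0.1814.

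- Shift s beyond baseline: the residual variance is 1−ρ² = 0.64 with gender and about 0.64 + 0.1814·s² without. The ratio of reported standard errors is √(1 + 0.1814·s²/0.64), which is 1.009 for s=0.25, 1.035 for s=0.5 and 1.133 for s=1.
- Stable difference D at both visits: without gender, total variance is V = 1 + 0.1814·D², covariance is C = 0.6 + 0.1814·D², and the residual variance is V − C²/V. For D=1 this is 1.1814 − 0.7814²/1.1814 = 0.6646, ratio √(0.6646/0.64) = 1.019. For D=0.5 it is 0.6469, ratio 1.005.

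**Simulation.** 20,000 trials per cell, stratified permuted blocks of 2, 4 or 6, with regression of post-intervention ST on arm and baseline ST, without and with gender. With two visits and complete data, this stands in for the constrained model without gender, and with gender plus gender-by-time. Results at ρ=0.6, without → with gender:

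| Gender effect | Mean SE | Type I error | Power |
|---|---|---|---|
| None | 0.2488 → 0.2490 | 5.0% → 5.0% | 64.4% → 64.2% |
| Stable, 0.5 SD | 0.2495 → 0.2484 | 4.8% → 4.8% | 64.4% → 64.5% |
| Stable, 1 SD | 0.2532 → 0.2488 | 4.5% → 4.7% | 63.1% → 64.4% |
| Beyond baseline, 0.25 SD | 0.2509 → 0.2488 | 5.0% → 5.1% | 64.0% → 64.5% |
| Beyond baseline, 0.5 SD | 0.2578 → 0.2488 | 4.2% → 4.9% | 62.2% → 64.7% |
| Beyond baseline, 1 SD (extreme) | 0.2831 → 0.2488 | 3.0% → 5.1% | 54.3% → 64.7% |

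The simulated SE ratios agree with the closed form (for example 0.2578/0.2488 = 1.036 against 1.035). Each power figure has a Monte Carlo standard error of about √(0.64 × 0.36/20,000) = 0.3 points. The mean null estimate stayed within 0.003 SD of zero, and null rejection without gender never exceeded 5.1%.

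A repeat of the 0.5 SD beyond-baseline case shows the mechanism. The true (empirical) SE was 0.251 in both models, while the reported SE was 0.258 without gender and 0.249 with it. The estimate is equally precise either way; only the reported uncertainty differs.

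**Range.** Power gains in points at ρ = 0.4 / 0.6 / 0.8:

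- stable 0.5 SD: 0.6 / 0.1 / −0.1
- stable 1 SD: 2.4 / 1.3 / 0.5
- beyond baseline 0.5 SD: 2.0 / 2.5 / 4.9
- beyond baseline 1 SD: 7.5 / 10.4 / 17.8

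**Second parameterisation.** Here the smaller stratum is 20% or 30% of participants, the correlation is 0.5, and gender explains a share R² of the variance left after baseline. The reported SE exceeds the true SE by 1-2%, 4% and 9% at R² of 5%, 10% and 20%. Type I error is about 4.6%, 4.0-4.3% and 3.2-3.4%. About 1, 3 and 6 power points are lost, starting from about 80%.

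**The case against.** The strongest reply is that the condition for harm has no support in the documents and the likely loss is close to nil. Baseline ST is already in the model, and the gap between visits is short: the post-intervention measurement is at 3 weeks, with baseline wear completed before randomisation. A stable gender difference is therefore mostly absorbed. For a stable 0.5 SD difference at ρ=0.6 the gain is 0.1 points, the same order as the cost of adjusting for an irrelevant factor. This stands, and it is why the point is a low-cost improvement rather than a flaw that threatens the trial.

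The large figures need extreme inputs. A 1 SD shift beyond baseline means gender explains 0.1814/(0.1814 + 1 − ρ²) of the variance left after baseline: 18%, 22% and 34% at ρ = 0.4, 0.6 and 0.8. Nothing in the documents suggests that, so those rows are an outer bound only.

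The assumed effect also exceeds the only effect size in the documents, d = 0.3. At 0.3 SD and ρ=0.6, power without and with gender is 21.7% and 22.0% (stable 0.5 SD), 20.8% and 21.5% (stable 1 SD), and 20.0% and 21.9% (beyond baseline 0.5 SD). The pattern is the same; the gains are somewhat smaller.

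Two cautions also stand. The absence of bias was checked with complete data only, whereas SAP 4.3 and 6.3 expect some missing values. And the SAP already reports 42 participants included, with a research team not blinded to allocation, so a covariate added late could look like a choice made after seeing results. Neither shows that gender should be left out; the second makes the date of the change important.

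**Conclusion.** The point holds. The stratum is in no planned model, no reason is given, and if gender predicts post-intervention ST beyond baseline ST, the reported standard error is too large and some power is lost. Any error is conservative.

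Under the assumptions above, the loss is about 0 to 2.4 power points for a stable gender difference of 0.5 to 1 SD, and 2.0 to 4.9 points for a 0.5 SD shift beyond baseline, over correlations of 0.4 to 0.8. The size rests on the assumed gender split, correlation and gender effect. The direction does not. The reason to act is the balance of cost and gain: adjusting costs at most 0.3 points if gender is irrelevant, and the analysis then follows the randomisation.

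**What to change.** In SAP 6.2, for the primary and continuous secondary outcomes, name the model terms as: time (categorical), gender, gender-by-time, and the group effect at post-intervention, with the arms constrained equal at baseline. Both gender terms are needed. A main effect alone forces the same gender difference at both visits and captures only part of the effect on the post-intervention value given baseline.

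Date the change before analysis. If analysis has already begun, keep the planned model as primary and label the gender-adjusted one as added later.

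For the logistic mixed model of ST of at least 9.5 h/day, make gender optional. Adding it changes the odds ratio to one conditional on gender, and cells may be sparse. With 10 people in the smaller stratum split five and five and a prevalence of 50%, the chance of an empty arm-by-outcome cell is 1 − (1 − 2 × 0.5⁵)² = 12%. Simulation allowing for uneven blocks gives 13%, rising to 23% (prevalence 50% v 30%) and 40% (40% v 20%). With 6 people it is 46% to 67%. If gender is used there, prespecify the model without it as the fallback and state which odds ratio is reported.

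The cost is one SAP sentence and one or two degrees of freedom in the linear models. Gender is already collected.

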## 6.3 Missing data

The number of missing data will be reported, and patterns of missing data will be explored. Based on previous experience, we expect that missing data will be assumed as missing at random. Therefore, the linear mixed model analyses will handle our missing data. However, once the data processing is finalized, we reconsider this assumption. In case we believe this assumption does not hold, we will take appropriate measures for the data analyses by using e.g. other multiple imputation techniques.

## 6.4 Additional analyses

To assess the presence of potential selection bias among study participants, sedentary behavior and physical activity characteristics at 3 months post-CR (i.e. last assessment of previous RCT) will be compared between our analytical cohort and non-participants using an independent samples t-test (continuous normally distributed data), Wilcoxon-signed rank test (continuous not-normally distributed data) or  $\chi^2$  test (categorical data).

To assess the long-term effects of CR on sedentary behavior and PA characteristics taking into account the results of the original SITLESS, linear (continuous data) and logistic (categorical data) mixed-model analyses with time as a categorical variable will be used. The BOOSTSITLESS is taken as reference and compared to measurements at pre-CR, post-CR and 3 months post-CR measurements of the previous (SITLESS) RCT.

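### SAP 6.4 names a paired test, the Wilcoxon signed-rank, for comparing two independent groups: participants and non-participants

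*SAP*

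**What the plan says.** SAP 6.4 (Additional analyses) opens with a check for selection bias. The values used are those recorded "at 3 months post-CR (i.e. last assessment of previous RCT"). According to the SAP, these measures of sitting and activity "will be compared between our analytical cohort and non-participants using an independent samples t-test" or one of two alternatives, depending on the type of data. The three branches are:

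- normal continuous data: "independent samples t-test (continuous normally distributed data");
- non-normal continuous data: "Wilcoxon-signed rank test (continuous not-normally distributed data");
- categorical data: a chi-squared test.

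Neither document describes matching participants to non-participants. SAP 4.1 adds a general rule for all analyses: "P for significance will be set at 0.05 and 95% confidence intervals will be estimated".

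**The concern.** The signed-rank test works on differences within pairs, or on one sample against a fixed value. Someone from the SIT LESS arm is either in the analytical cohort or a non-participant, never both, and the comparison uses a single measurement occasion. There is therefore no pair to take a difference from. The t-test named in the same sentence treats the groups as independent, so two branches of one comparison assume different data structures.

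What is at stake is the selection check itself. SAP 3.3 gives 42 included participants from an arm planned at 106, so readers will use this comparison to judge how well the participants represent SIT LESS graduates. For any non-normal characteristic, the analyst would have to depart from the SAP or pair unrelated people.

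**Working it through.** The SAP states no figure to reproduce on this point. The check is whether the named test fits the data described, followed by how much of the analysis it touches.

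**1. Data structure (SAP 6.4)**

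| Feature | What SAP 6.4 describes | Signed-rank test | Rank-sum test |
|---|---|---|---|
| Groups | Two disjoint sets of people | Needs one set, or matched pairs | Fits |
| Occasions | One | Needs two values per person or pair | Fits |
| Matching | None described | Required between different people | Not needed |
| Equal numbers | Not assured | Required | Not needed |

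**2. Could another part of the SAP account for the name?** SAP 6.2 covers only the randomised comparison and uses mixed models. The second paragraph of SAP 6.4 does have repeated measures on the same people, but it assigns mixed models to them. SAP 6.6 names R and gives no function for this check. Nothing corrects or explains the signed-rank test.

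**3. How many variables could reach this branch?** SAP 6.4 does not list the characteristics, so I take them from the outcomes in SAP 6.1. Five are continuous: sedentary time, prolonged sedentary bouts, light activity, moderate-to-vigorous activity and steps (the last listed as "Change in step count (steps/day; baseline and post-intervention")). One is categorical, the 9.5 h/day cut-off, counting its two entries as a single item. That gives 5 + 1 = 6, of which 0 to 5 could be non-normal.

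**4. Can it be computed?** A paired call needs equal numbers of values in the two groups. SAP 3.3 refers to "the included sample size (n=42) is large enough to run meaningful analyses" and says that "106 patients were needed in the SIT LESS arm of the trial". The documents do not give the number of non-participants with three-month data; call it m. Assuming all 42 participants have three-month data, the number of people left without a partner is |m − 42|:

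- m = 40: 42 − 40 = 2
- m = 50: 50 − 42 = 8
- m = 64, which is 106 − 42 if the arm reached its planned size and everyone has data: 64 − 42 = 22

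On simulated skewed data at these three sizes, the signed-rank test stopped with an unequal-length error each time and the rank-sum test ran each time. In R, a paired call on groups of 42 and 64 stops because the two vectors differ in length; the unpaired call returns the Wilcoxon rank-sum test.

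**5. If the sizes happened to match.** The paired call would run, but the pairs would be set by row order. Re-sorting one group could change the result, so it would say nothing about selection.

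**The case against.** The best reply is that this is a slip in terminology. The sentence speaks of comparing two groups and names the unpaired t-test, so the intent is plain. R's unpaired Wilcoxon function performs the rank-sum test anyway. A competent analyst would very likely run the right test and correct the name in the report; pairing unrelated people is a remote prospect. That is fair, and it is a reason to rate the point minor. It does not make the SAP correct: the test that would be run is not the one pre-specified, and the SAP and the published paper would disagree.

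The illustrative numbers can also be challenged. The 106 is a planned size, not the number enrolled or with three-month data, and SAP 5.3 restricts the eligible pool to people who did not drop out of SIT LESS. Not all 42 participants need have the three-month measurement. The list of characteristics is inferred from the trial outcomes. All of this stands, but the conclusion needs none of these figures: the test is wrong because no pairs exist, whatever the group sizes.

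Finally, a Hodges-Lehmann interval goes beyond correcting the error. That is true, and it is offered below as an optional addition.

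**Conclusion.** The concern holds. The non-normal branch of the selection check in SAP 6.4 names a test that does not fit the comparison and cannot be validly carried out as written. The severity is minor. The error occurs once, in an additional descriptive analysis, and affects between none and five of six characteristics, taking the list from SAP 6.1. The other two branches of the check, the mixed models in SAP 6.2 and the randomised treatment estimate are unaffected. The conclusion rests only on the two groups being disjoint, unmatched and measured once, all of which follows from SAP 6.4.

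**What to change.** In SAP 6.4, replace the Wilcoxon signed-rank test with the Wilcoxon rank-sum (Mann-Whitney U) test for continuous variables that are not normally distributed. This changes one test name and needs no new data.

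It would also help to report the size of the participant versus non-participant differences with the 95% confidence intervals that SAP 4.1 already plans. For the rank-sum branch that would be the Hodges-Lehmann shift and its interval. The point is corrected without this addition.
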